EPI	Expanded Program on Immunization
FDA	Food and Drug Administration
FWA	Federal Wide Assurance
GCP	Good Clinical Practice
GLP	Good Laboratory Practices
GMT	Geometric Mean Titer
HepB	Hepatitis B virus vaccine
Hib	Haemophilus influenzae type b conjugate vaccine
IATA	Health Insurance Portability and Accountability Act
ICF	Informed Consent Form
ICH	International Conference on Harmonisation
ID	Identification
IDCRC	Infectious Disease Clinical Research Consortium
IDE	Investigational Device Exemption

IEC	Independent or Institutional Ethics Committee
IM	Intramuscular
IND	Investigational New Drug Application
IPV	Inactivated Polio Vaccine, parenteral
IRB	Institutional Review Board
ISM	Independent Safety Monitor
MAAE	Medically-Attended Adverse Event
MedDRA [®]	Medical Dictionary for Regulatory Activities
MenA	Monovalent meningococcal serogroup A conjugate vaccine, MenAfriVac [®]
MenACYW-TT	Quadrivalent meningococcal conjugate vaccine, Nimenrix [®]
MM	Medical Monitor
MO	Medical Officer
MOP	Manual of Procedures
MR	Measles-Rubella Vaccine
MVP	Meningitis Vaccine Project
N	Number (typically refers to subjects)
NDA	New Drug Application
NIAID	National Institute of Allergy and Infectious Diseases, NIH
NIBSC	National Institute for Biological Standards and Control
NIH	National Institutes of Health, DHHS
NmC	Serogroup C
NmCV-5	Meningococcal (A,C,Y,W,X) polysaccharide conjugate vaccine
NmW	Serogroup W
NmX	Serogroup X
NRA	National Regulatory Agency
OER	Office of Extramural Research
OHRP	Office for Human Research Protections
OPV	Oral Polio Vaccine
PCV	Pneumococcal Conjugate Vaccine
PEI	Paul Ehrlich Institute
PHE	Public Health England
PHI	Protected Health Information
PI	Principal Investigator
PP	Per Protocol
PQ	Pre-Qualification
PS	Polysaccharides
QA	Quality Assurance
QC	Quality Control
rSBA	Rabbit complement serum bactericidal antibody
SA	Secondary Aims
SAE	Serious Adverse Event/Serious Adverse Experience
SAGE	WHO's Strategic Advisory Working Group of Experts
SAP	Statistical Analysis Plan

SCHARP	Statistical Center for HIV/AIDS Research & Prevention, at Fred Hutchinson Cancer Research Center
SDCC	Statistical and Data Coordinating Center
SDSU	Statistical and Data Science Unit
SIPL	Serum Institute of India Pvt Ltd.
SOC	System Organ Class
SOP	Standard Operating Procedure
SUSAR	Suspected Unexpected Serious Adverse Event
TT	Tetanus Toxoid
UKHSA	UK Health Security Agency
US	United States
VTEU	Vaccine and Treatment Evaluation Unit
WHO	World Health Organization
YF	Yellow Fever vaccine

PROTOCOL SUMMARY

- Title:** A Phase 3 Trial to Evaluate the Safety, Immunogenicity, and Non-Interference with Concomitant Routine Vaccines, of a Meningococcal Serogroup ACYW-X Conjugate Vaccine (NmCV-5) in Comparison with MenACWY-TT Conjugate Vaccine in Healthy Malian Infants
- Design of the Study:** This trial will evaluate a single dose of NmCV-5 administered at either 9 months or 15 months of age, time points in the Expanded Program on Immunization (EPI) schedule when meningococcal vaccine is most likely to be administered. Infants aged 9 months will be consented and randomized to the assigned age group to receive vaccine at 9 months or 15 months. Infants aged 9 months (eligibility 9-11 months) and randomized to the 9-month age group will be randomized in a 2:1 ratio to receive a single dose of NmCV-5 or a single dose of MenACWY-TT. Prospectively identified and consented infants randomized to the 15-month age group will return when aged 15 months (eligibility 15-17 months) and will be randomized in a 2:1 ratio to receive a single dose of NmCV-5 or a single dose of MenACWY-TT. “Enhanced” EPI vaccines will be co-administered and will consist of 2-doses of a measles and rubella-containing vaccine administered at 9 months and 15 months and a single dose of yellow fever vaccine administered at 9 months.
- Study Rationale:** Progressive introduction of MenAfriVac since 2010 has resulted in a substantial reduction in cases of serogroup A meningococcal disease. However, regular large-scale epidemics due to serogroups C, W and X remain common in the African meningitis belt. An affordable and scalable pentavalent meningococcal conjugate vaccine (NmCV-5) has been developed by SIPL, the manufacturer of MenAfriVac. NmCV-5 is designed to protect against serogroups A, C, W, Y and X. The immediate goal for the clinical development of NmCV-5 is for WHO Pre-Qualification (WHO-PQ), to enable the vaccine to be used in the Meningitis Belt of sub-Saharan Africa.
- The current Phase 3 study, as agreed under the WHO-PQ strategy, is a study of NmCV-5 in the infant Expanded Program on Immunization (EPI) schedule in sub-Saharan Africa. This

study protocol is designed to provide evidence that concomitant vaccination with NmCV-5 will not significantly affect the immune responses of infants to their normally scheduled EPI vaccines. We have specifically designed this study to provide information at two distinct timepoints, 9 months and 15 months. The WHO-PQ quadrivalent meningococcal conjugate vaccine MenACWY-TT (Nimenrix®, manufactured by Pfizer) is to be the control comparator vaccine to NmCV-5. MenACWY-TT is approved for use in infants as young as 6 weeks of age. WHO supports the evaluation of the age ranges of 9 months and 15 months under which NmCV-5 is intended to be adopted by stakeholder countries in the Meningitis Belt.

The current Mali EPI schedule consists of a measles only vaccine, yellow fever vaccine, and MenA vaccine at 9 months of age; there is no 15 months of age EPI vaccine visit and typically only a single dose of a measles-containing vaccine is administered. However, to satisfy the conditions for WHO-PQ, study participants will receive two doses of a measles-containing vaccine, at 9-months and 15-months. Furthermore, the non-inferiority evaluation must include an assessment of the rubella vaccine responses. These modifications to the standard Malian EPI schedule provide a level-of-care that is higher than the current standard-of-care for the general population. Within the context of this study, we will refer to this as an “enhanced” EPI schedule.

Study Phase:	3
Study Population:	Healthy infants aged 9-11 months who reside in Bamako, Mali.
Number of Sites:	1
Description of Study Products:	NmCV-5 (the experimental meningococcal vaccine) is a pentavalent meningococcal (A, C, Y, W, X) polysaccharide-conjugate vaccine composed of capsular polysaccharides (PS) from Neisseria meningitidis serogroups A, C, Y, W, and X individually conjugated to a protein carrier, either mutant diphtheria toxoid (CRM ₁₉₇) or tetanus toxoid (TT).

MenACWY-TT (the comparator meningococcal vaccine) is a WHO-PQ quadrivalent meningococcal (A, C, Y, W) polysaccharide-conjugate vaccine manufactured by Pfizer (known as Nimenrix®).

“Enhanced” EPI Vaccines:

The combined measles-rubella (MR) vaccine is WHO-PQ and manufactured by SIPL.

The yellow fever (YF) vaccine is WHO-PQ and manufactured by Sanofi Pasteur (Stamaril®).

Primary Objectives	Primary Endpoints

 • To demonstrate that the immune responses to meningococcal serogroups A, C, Y, W, and X elicited by one dose of NmCV-5 at 9 months of age are non-inferior to the immune responses to meningococcal serogroups A, C, Y, W elicited by one dose of MenACWY-TT at 9 months of age, as measured by rabbit serum bactericidal antibody (rSBA) titers at 28 days after vaccination, and when meningococcal vaccines are given concomitantly with routine vaccines. • To demonstrate that the immune responses to meningococcal serogroups A, C, Y, W, and X elicited by one dose of NmCV-5 at 15 months of age are non-inferior to the immune responses to meningococcal serogroups A, C, Y, W elicited by one dose of MenACWY-TT at 15 months of age, measured by rSBA titers at 28 days after vaccination, and when meningococcal vaccines are given concomitantly with routine vaccines. 	
 • The percentage of participants with seroprotective response (rSBA antibody titers ≥ 8) against each meningococcal serogroup A, C, W and Y in the NmCV-5 arm, 28 days after a single dose of meningococcal vaccine, relative to the percentage of participants with seroprotective response against each serogroup A, C, W and Y in the MenACWY-TT arm, among participants vaccinated at either 9 months or 15 months of age. The percentage of participants with seroprotective response to serogroup X in the NmCV-5 arm, to be compared to the percentage of participants with the lowest seroprotective response among serogroups A, C, W and Y in the MenACWY-TT arm.
Secondary Objectives	Secondary Endpoints

 • To assess the safety and tolerability of a single dose of NmCV-5 or MenACWY-TT, when given concomitantly with routine vaccines. 	
 • All Serious Adverse Events (SAE), reported during the first 6-months of follow-up period after meningococcal vaccination. • All solicited AEs reported during a 7-day follow-up period after meningococcal vaccination. Solicited AEs include injection

	
site tenderness, injection site swelling/induration, injection site erythema, irritability, drowsiness, anorexia, vomiting, fever, and feverishness.
 
 All unsolicited AEs reported through 28 days after meningococcal vaccination.

 To demonstrate that the immune responses to meningococcal serogroup X elicited by one dose of NmCV-5 (at either 9 or 15 months of age) is superior to that elicited by MenACWY-TT (at either 9 or 15 months of age) measured by rSBA titers at 28 days after vaccination. 	
 The percentage of participants with seroprotective response (rSBA antibody titers ≥ 8) to serogroup X in the NmCV-5 arm compared to the percentage of participants with seroprotective response to serogroup X in the MenACWY-TT arm, 28 days after a single dose of meningococcal vaccine.

 To demonstrate the non-inferiority of the immune responses to EPI vaccines (measles-rubella, yellow fever, measles booster) when co-administered with NmCV-5 (at either 9 or 15 months of age) compared to the immune responses when co-administration with MenACWY-TT (at either 9 or 15 months). 	
 Proportion of participants with seropositive response for measles and rubella, and seroprotective titers for yellow fever vaccine. The seropositive response to measles vaccine is defined as anti-measles IgG concentration > 200 mIU/mL, at Day 29. The seropositive response to rubella vaccine is defined as anti-rubella IgG concentration >20 IU/mL, at Day 29. The seroprotective response to yellow fever vaccine is defined as yellow fever neutralizing antibody titers $\geq 1:10$.

 To assess clinically significant immune response indicators elicited by a single dose of NmCV-5, given concomitantly with routine vaccines, as compared to those elicited by MenACWY-TT. 	
 Level of rSBA titers (GMTs) against meningococcal serogroups A, C, W, X and Y at 28 days after a single dose of meningococcal vaccine at either 9 or 15 months of age. Percentage of participants with seroresponse* in rSBA titers to meningococcal serogroups A, C, W, X and Y at 28 days after a single dose of meningococcal vaccine at either 9 months or 15 months of age (subset of participants). 
*Seroresponse is defined as a post-immunization (Day 29) rSBA titer of 32 or greater if the participant's pre-immunization (Baseline) rSBA titer was < 8; or a \geq four-fold increase over baseline at Day 29 post-immunization if the participant's pre-immunization rSBA titer was ≥ 8.

	
 Number and proportion of participants with rSBA titers ≥ 128 at 28 days after a single dose of meningococcal vaccine.
Tertiary Objective	Tertiary Endpoint

 To assess the safety of a single dose of NmCV-5 or MenACWY-TT through 2 years of follow-up after meningococcal vaccination. 	
 All SAEs, reported through 2 years of follow-up or during the entire study period.

 To assess the persistence of the immune responses at 6 months and 2 years after meningococcal vaccination. 	
 The number and proportion of participants with rSBA titers ≥ 8 and ≥ 128 and the calculated rSBA GMTs against each of the five meningococcal serogroups at 6 months and 2 years following meningococcal vaccination.
Exploratory Objectives	Exploratory Endpoints

 To compare the immune responses of the 9-month and 15-month group against each of the five meningococcal serogroups at Day 29. 	
 The comparison of the 9-month and 15-month group proportions of seroprotective response rates and rSBA GMTs against each of the five meningococcal serogroups at Day 29.

Study Eligibility Criteria:

Inclusion Criteria:

1. Male and female children between 9 months and 11 months old inclusive.
2. Parent(s)/legal guardian(s) have provided written informed consent, after the nature of the study has been explained according to local regulatory requirements.
3. The investigator believes that their parent(s)/guardian(s) will be available for all the subjects visits and will comply with the requirements of the protocol (e.g., timely reporting of adverse events).
4. Individual is in good health as determined by medical history, physical examination, and clinical judgement of the investigator. *(Note: the physical examination may have been performed on a separate screening day and will be considered valid if within 14 days of enrollment)*
5. Individual has completed their local infant EPI vaccines, not including 9-month EPI vaccines (at the 9-month visit) or 15-month EPI vaccines (at the 15-month visit). A birth dose of oral polio vaccine is not required.

Exclusion Criteria:

1. History of receipt of any meningococcal vaccine.
2. Has received a measles-containing vaccine.
3. Current or previous, confirm or suspected disease caused by *N. meningitidis*.
4. Household contact with and/or intimate exposure to an individual with any laboratory confirmed *N. meningitidis* infection within 60 days of enrolment or study vaccination (for the 15-month age group).
5. History of severe allergic reactions after previous vaccinations or hypersensitivity to any study vaccine component including tetanus, diphtheria and mutant diphtheria toxoid (CRM₁₉₇).
6. Acute or chronic, clinically significant pulmonary, cardiovascular, metabolic, neurological, hepatic, or renal functional abnormality, as determined by medical history or physical examination.
7. Any confirmed or suspected condition with impaired or altered function of the immune system (e.g., immunodeficiency, autoimmune conditions, malnutrition).
8. Have any bleeding disorder which is considered a contraindication to intramuscular injection or blood draw.
9. Severe acute malnutrition. *Note: a weight-for-length Z-score of less than -3 satisfies this exclusion criteria.*
10. History of either hepatitis B or hepatitis C virus infection, human immunodeficiency virus infection, or hereditary immunodeficiency.
11. Presence of major and clinically significant congenital defects.
12. Chronic administration (defined as more than 14 days) of immunosuppressants or other immune-modifying drugs within three months prior to the study vaccination or planned use throughout the study period (for corticosteroids, this means prednisone, or equivalent, ≥ 0.5 mg/kg per day. Inhaled, intranasal, and topical steroids are allowed).
13. Administration of blood, blood products and/or plasma derivatives or any parenteral immunoglobulin preparation in the past 3 months or planned use throughout the study period.

14. Administration of any vaccine within 14 days prior to enrolment in the study or planned administration of any vaccine within 14 days before or after study vaccination.
15. Use of any investigational or non-registered drug or vaccine within 28 days prior to the administration of study vaccine or planned during the study.
16. Malaria infection as confirmed by a Rapid Diagnostic Test.
Note: subjects positive at screening may be treated for malaria as per national guidelines outside of the study, and if the subject remains eligible, vaccinated no earlier than 5 days after completing treatment.
17. Individuals who are close family member* of individuals conducting this study. **defined as a child with direct genetic relationship to a member of the study team.*
18. Have experienced a moderate or severe acute infection and/or fever (defined as temperature $\geq 37.5^{\circ}\text{C}$) within 3 days prior to enrolment or study vaccination.
19. Have received systemic antibiotic treatment within 3 days prior to enrolment or study vaccination.
20. Non-residence in the study area or intent to move out within six months.
21. Any condition which, in the opinion of the investigator, might pose additional risk to the subject due to participation in the study.

[figure not shown]
**Duration of Individual
Subject Participation:**

Approximately 24 or 30 months

**Estimated Time to Last
Subject/Last Study Day:**

Approximately 4 years

Figure 1: Schematic of Study Design

Schedule of Events

Group 1: Participant Age (9-month group)	9 mon	9 mon	9 mon	10 mon	15 mon	33 mon	
Visit	Screen	Visit 1	Visit 2	Visit 3	Visit 4	Visit 5	ET
Study Day		1	8	29	181	730	
Window			+3	+7	±14	±45	
Informed Consent	X						
Demographics ¹	X						
Medical History including review of systems ¹	X						
Determination / Confirmation of Eligibility	X	X					
Rapid Diagnostic Test for malaria		X					
Photo of child		X					
Vital Signs ^{1,2} including axillary temperature	X		X	X	X	X	(X)
Height, weight ¹	X						
Physical exam ¹	X		X	X	X	X	(X)
Randomization Step 1	X						
Randomization Step 2		X					
Blinded Vaccination		X					
Administration of enhanced EPI vaccines [†]		X			X		
30-minute observation period post meningitis vaccination		X					
7-day Memory Aid (d ispense & c ollect) ⁴		D	C				

AE assessment		X	X	X			(X)
Concomitant medications and vaccinations ^{1,3}	X	X	X	X			X
SAE assessment		X	X	X	X	X	X
Research Blood Draw (mL)		5 mL		10 mL	5 mL	5 mL	5 mL

Group 2: Participant Age (15-month group)	9 mon	15 mon	15 mon	16 mon	21 mon	39 mon	
	Screen	Visit 1	Visit 2	Visit 3	Visit 4	Visit 5	ET
Visit							
Study Day		1	8	29	181	730	
Window			+3	+7	±14	±45	
Informed Consent	X						
Demographics ¹	X						
Medical History including review of systems ¹	X	X					
Determination / Confirmation of Eligibility	X	X					
Rapid Diagnostic Test for malaria		X					
Photo of child		X					
Vital Signs ^{1,2} including axillary temperature	X	X	X	X	X	X	(X)
Height, weight ¹	X	X					
Physical exam ¹	X	X	X	X	X	X	(X)
Randomization Step 1	X						
Randomization Step 2		X					
Blinded Vaccination		X					
Administration of enhanced EPI vaccines [†]	X	X					
30-minute observation period post meningitis vaccination		X					
7-day Memory Aid (d ispense & g ollect) ⁴		D	C				
AE assessment		X	X	X			(X)
Concomitant medications and vaccinations ^{1,3}	X	X	X	X			X
SAE assessment		X	X	X	X	X	X
Research Blood Draw (mL)		5 mL		10 mL	5 mL	5 mL	5 mL

†, Enhanced EPI vaccines at 9-months consist of measles-rubella (MR) and yellow fever (YF) vaccine; the Enhanced EPI vaccine at 15-months consists of MR vaccine.

¹ Conducted after consent obtained.

² Vital signs include heart rate and respiratory rate.

³ Concomitant medication and vaccination history will be updated at study visits through Day 29.

⁴Field workers will visit homes as described in Section 5.4.

() As applicable

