2 STUDY DESIGN, OBJECTIVES AND ENDPOINTS OR OUTCOME MEASURES

2.1 Study Design Description

Infants aged 9 months (eligibility 9-11 months) will be consented, enrolled at Step 1, and randomized. A first-step randomization at a 1:1.2 ratio will determine whether the infant will receive blinded meningococcal study product at the 9-month (Group 1, n=600) or the 15-month (Group 2, n=720) enhanced EPI vaccination visit. Within the 9-month or 15-month age groups, a second-step randomization at a 2:1 ratio will determine whether the study participant will receive a single dose of NmCV-5 (Group 1A or 2A) or a single dose of control vaccine, MenACWY-TT (Group 1B or 2B). The infant will be considered enrolled upon the successful first step randomization of the study, which will occur at the time of presenting to their 9-month EPI visit.

If the randomized study product is to be administered at the 15-month visit, the prospectively identified and consented infants will complete their designated “enhanced” EPI immunizations at the 9-month visit, except no meningococcal vaccine will be administered. At their 15-month visit (eligibility 15-17 months), these infants will receive a single dose of NmCV-5 or a single dose of control vaccine, as per the second-step randomization at a 2:1 ratio. Because we anticipate up to 20% of infants may be lost to follow-up (i.e., fail to return to the clinic for their 15-month visit) or may become ineligible (e.g., receives MenAfriVac prior to the 15-month visit), there is the plan to over randomize study infants into the 15-month group—this is the underlying reason for the first-step randomization at 1:1.2. Upon successful randomization of 600 eligible infants into the 15-month groups, all remaining prospectively identified infants (up to n=120) regardless of age upon return will be offered immunization with MenACWY-TT and the “enhanced” EPI vaccinations from available study supply, but otherwise are no longer eligible for the study (i.e., will not be followed in the context of this study). If “enhanced” EPI vaccinations are declined or not available, infants will be referred to local clinic for standard EPI vaccination.

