- Medical interview of subject's parents/guardians to determine if any SAEs occurred since the last study visit.
- Physical examination including assessment of heart rate, respiratory rate, and axillary body temperature
- Collection of blood sample (approximately 5 mL) for serology testing.
- For participants randomized and enrolled in the 9-month groups, a measles-rubella containing vaccine will be administered at this 15-month old visit.
- Schedule Visit 5, approximately 2 years after vaccination

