5.3.3 Early Termination Visit

A subject may discontinue study participation at any time prior to the last planned study visit. This is referred to as an early termination from the study. The reasons for early termination from the study include: adverse event, death, withdrawal of consent, lost to follow-up, administrative reason, protocol deviation, or other reasons upon the investigator's judgement. The investigator should make every effort to investigate whether or not safety concerns (adverse event, SAE or death) may have been related to the subject's discontinuation from the study. If a safety concern has been associated with the subject's discontinuation, this must be described on the Termination electronic case report form (eCRF) page, even if it is not the primary reason for the subject's discontinuation.

When possible, an early termination clinic visit should be performed so that a PE including assessment of vital signs and axillary temperature, can be performed and the collection of blood (approximately 5 mL) may be possible. Concomitant medications and vaccinations may be collected through Day 29.

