6 DESCRIPTION OF CLINICAL AND LABORATORY EVALUATIONS

6.1 Clinical Evaluations

Complete medical history will be obtained by interview of subjects on the day of study vaccination prior to the study vaccination. Subjects will be queried regarding a history of significant medical disorders of the head, eyes, ears, nose, throat, mouth, cardiovascular system, lungs, gastrointestinal tract, liver, pancreas, kidney, urologic system, nervous system, blood, lymph nodes, endocrine system, musculoskeletal system, skin, and genital/reproductive tract. A history of any allergies, cancer, immunodeficiency, and autoimmune disease will be solicited. At follow-up visits after the study vaccination, an interim medical history will be obtained by interview of subjects noting any changes since the previous clinic visit or contact. All concomitant medications and an updated vaccination history will also be collected through Day 29.

At the Day 1 visit prior to the study vaccination, a physical examination will be performed on all subjects to include the following organs and organ systems: including skin, head and neck, lungs, heart, liver, spleen, extremities, lymph nodes, and nervous system, by a study clinician (site principal investigator or sub-investigator). At follow-up visits after the first study vaccination, a targeted physical examination may be performed, if indicated based on the subject's interim medical history, by a study licensed clinician as the site principal investigator or sub-investigator. Targeted physical examinations should also include an assessment for any adverse events.

Vital signs (heart rate and respiratory rate) and axillary body temperature will be collected prior to study vaccination and at follow-up visits.

Height and weight will be collected at the Day 1 visit prior to the first study vaccination for the assessment of nutritional status age Z-score (HAZ/LAZ).

Subjects will be observed in the clinic for at least 30 minutes after receiving the study meningitis vaccination. The study vaccination site will be examined, post-administration reactogenicity assessments will be performed, and any AE/SAEs will be recorded on the appropriate data collection form prior to discharge from the clinic.

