### **3.2.4 Durability Immunogenicity Analysis Sets**

These analysis sets will assess the longer-term durability of meningitis immunogenicity based on rSBA titers from blood samples collected at the Day 181 ( $\pm 14$  days) and Day 730 ( $\pm 45$  days) study visits. At the time of the finalization of this SAP, these sets are intended to include up to 300 participants from each of Group 1 and Group 2 (200 from the NmCV-5 arm and 100 from the MenACWY-TT arm in each group).

These sets will include participants who:

- Are included in both the Baseline Immunogenicity Analysis Set and the Per Protocol Analysis Set and had blood collected at the Day 181 ( $\pm 14$  days) or Day 730 ( $\pm 45$  days) study visits (Part A), or
- Are randomly chosen from those participants in the Per Protocol Analysis Set (not included in Part A) who had blood collected at the Day 181 ( $\pm 14$  days) or Day 730 ( $\pm 45$  days) study visits (Part B, with enough randomly selected participants to complete the sample of 300 participants per study group after determining the participants in Part A).

If future circumstances allow for assaying of all collected samples, the Durability Immunogenicity Analysis Set will include all participants in the Per Protocol Analysis Set with blood samples collected at Study Day 181 ( $\pm 14$  days) or Study Day 730 ( $\pm 45$  days).

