#### 8.4 Tertiary Immunogenicity Analysis

- Objective:** To assess the persistence of the immune responses at 6 months and 2 years after meningococcal vaccination.
- Endpoints:** rSBA titers against meningococcal serogroups A, C, W, X and Y, from samples collected at Visit 4 (Study Day 181, approximately 6 months after meningococcal vaccination) and Visit 5 (Study Day 730, approximately 2 years after meningococcal vaccination).
- Analysis Set:** Durability Immunogenicity Analysis Set
- Approach and reporting:** For each of the five serogroups (A, C, W, X, Y), descriptive summaries for rSBA titers at Day 181 and Day 730 will be tabulated by vaccine arm. These will include:
- Geometric Mean Titers (GMT), with 95% confidence intervals.
  - Range.
  - Number and percentage of participants with rSBA titers  $\geq 8$ .
  - Number and percentage of participants with rSBA titers  $\geq 128$ .
  - Geometric Mean Fold Rise (GMFR) from baseline, with 95% CI, for those participants in the Baseline Immunogenicity Analysis Set.

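### Vaccination history stops at Day 29, so a non-study meningococcal dose given before the Day 181 or Day 730 sample would be counted as persistence of the study vaccine

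*Protocol*

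**What the plan says.** Every place in the protocol that deals with vaccination history ends it at Day 29:

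- Schedule of Events, footnote 3 (Protocol Summary and Appendix A): "Concomitant medication and vaccination history will be updated at study visits through Day 29". The row for concomitant medications and vaccinations is blank at Visits 4 and 5.
- Section 6.1: "All concomitant medications and an updated vaccination history will also be collected through Day 29".
- Section 5.3.3, early termination: "Concomitant medications and vaccinations may be collected through Day 29".

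The Visit 4 list (Section 5.3.1) has an interview of "parents/guardians to determine if any SAEs occurred since the last study visit", a physical examination and a blood draw, plus the second measles-rubella dose for Group 1. The Visit 5 list (Section 5.3.2) has the same interview, examination and blood draw.

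The tertiary objective in SAP 8.4 is "To assess the persistence of the immune responses at 6 months and 2 years after meningococcal vaccination". For it, "descriptive summaries for rSBA titers at Day 181 and Day 730 will be tabulated by vaccine arm". The Durability set (SAP 3.2.4) has two parts, both drawn from Per Protocol participants with blood taken at Day 181 or Day 730. Part A takes those who are also in the Baseline Immunogenicity set, and Part B takes participants who "Are randomly chosen from those participants in the Per Protocol Analysis Set (not included in Part A"). Neither section mentions a later meningococcal vaccine.

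**The concern.** Persistence means antibody still present from the one study dose. A child who receives another meningococcal vaccine between Day 29 and the sample no longer measures that. The titer would reflect the later dose, yet the child would appear in the durability table as if nothing had happened. The ≥8 and ≥128 proportions, the GMT and the fold rise from baseline would all move upward, and a real difference between arms would shrink. A dose that was never recorded cannot be excluded when the data are analysed.

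Outside vaccination is plausible. MenA is part of the routine 9-month visit in Mali (Protocol Table 3). Protocol 1.3.1 says that WHO allows it at any time from 9 to 18 months, so Group 1 children, about 10 months old at Day 29, remain in that window for months.

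**Working it through.** No figure in the plan depends on this point, so there is nothing to reproduce. The check has two parts.

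**1. What is observed, and what the analysis does with it**

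- Time without vaccination history: 181 − 29 = 152 days before the 6-month sample, and 730 − 29 = 701 days before the 2-year sample. The second is 701/729 = 96% of the interval from Day 1 to Day 730.
- Analysis: SAP 3.2.4 and 8.4 contain no exclusion, censoring or sensitivity analysis for an intervening dose.
- Indirect route: the last Per Protocol criterion (SAP 3.2.2) drops a child with a reported deviation judged able to affect meningococcal immunogenicity. It needs a report, and no visit after Day 29 prompts one. Protocol 5.6 defines a deviation as noncompliance with the protocol, GCP or MOP requirements. The protocol does not bar a later licensed meningococcal vaccine: exclusion 14 covers only 14 days either side of study vaccination, and exclusion 15 only investigational or non-registered products. An outside dose is therefore not clearly a deviation.
- Other form: the Termination Vaccination Status eCRF (SAP 6.2.3) is described only for Group 2 children not randomized to a study product.

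**2. Possible size, for illustration only**

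Inputs, neither of which is in the documents:

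- c, the share of children given an outside dose, assumed to be 2% to 10%.
- p, the true proportion with rSBA ≥8 at the later visit, assumed to be 60% or 90%.

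Assume that every child with an outside dose is at or above 8 for the serogroups in that vaccine, and that receiving it is unrelated to the child's own persistence. Then:

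observed proportion = p + c(1 − p), so bias = c(1 − p).

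| True p | c = 2% | c = 10% |
|---|---|---|
| 90% | 0.02 × 0.10 = 0.2 points | 0.10 × 0.10 = 1 point |
| 60% | 0.02 × 0.40 = 0.8 points | 0.10 × 0.40 = 4 points |

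The bias grows as persistence falls: p = 30% with c = 10% gives 0.10 × 0.70 = 7 points.

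For scale, the intended Durability set has 200 NmCV-5 and 100 MenACWY-TT children per age group. At p = 60% the approximate 95% half-width is 1.96 × √(0.6 × 0.4/200) = 6.8 points for n = 200 and 9.6 points for n = 100. At p = 50% and n = 200 the exact interval is 42.9% to 57.1%, so the bias of 0.5c exceeds the 7.1-point half-width only when c is above about 14%.

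If c is the same in both arms, a difference between arms is multiplied by (1 − c): 20 points becomes 18 at c = 10%.

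**The case against.** The strongest reply is that such doses should be rare. At study vaccination the child's card and medical record are marked to show a serogroup A vaccine (Protocol 5.2, Visits 1 and 1B), and the Malian schedule has one MenA dose. A repeat would need a clinic to overlook the card, or an off-schedule dose or a campaign, and the documents describe no campaign during follow-up. This stands as a reason to expect a small c. It does not detect a dose given anyway.

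A reader might infer from Protocol 2.1 that outside MenAfriVac is expected in vaccinated participants, because some infants "may become ineligible (e.g., receives MenAfriVac prior to the 15-month visit"). The text does not support that. It concerns Group 2 infants who have not yet had a study vaccine. They become ineligible, are not randomized at Step 2 and cannot enter the Durability set. The sentence shows only that MenAfriVac is available outside the study.

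Three other strong readings also fail:

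- That all five serogroups are materially distorted. MenAfriVac contains serogroup A only, and Protocol 1.1 says that no polyvalent conjugate is affordable at scale in the region and none addresses X. The other serogroups would need a multivalent outside dose, for which the documents give no evidence.
- That no vaccine after Day 29 is recorded. The study gives Group 1 the 15-month measles-rubella dose, and SAP 6.2.2 reports it.
- That an outside dose could never be detected or removed. One that a parent volunteers and the site logs as a deviation could be reviewed under SAP 3.2.2. That depends on chance, but the route exists.

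Parents are blinded to arm, so there is no evident reason for uptake to differ between arms.

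**Conclusion.** The gap is real and consistent across the schedule, the visit procedures and the SAP. As written, the plan would count a non-study meningococcal dose between Day 29 and the later samples as persistence of the study vaccine, mainly for serogroup A.

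Its size is unknown. Under the assumed ranges (c from 2% to 10%, p of 60% or 90%), the proportion with rSBA ≥8 is overstated by 0.2 to 4 points, and by more if persistence is lower. In that range the bias is smaller than the sampling error of the durability set. It is nevertheless systematic and upward, and it cannot be assessed without the data.

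Only the tertiary persistence endpoint is affected, and it is descriptive, with no test, margin or decision rule. The Day 29 primary and secondary results are untouched. This is an inexpensive improvement that would make the persistence claim verifiable; it does not threaten the trial's main conclusions.

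**What to change.** **Protocol.** Amend footnote 3 of the Schedule of Events and the procedures for Visit 4, Visit 5 and early termination (Sections 5.3.1 to 5.3.3), with Section 6.1 to match. At each of these visits, record any meningococcal vaccine received since Day 29, with its type and date, by parent interview and a check of the immunization card. The SAP shows that the study was already under way when it was written (3.2.3, 3.3.5), so where a visit has passed, collect the information retrospectively from the card.

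**SAP 3.2.4 and 8.4.** State that samples taken after a non-study meningococcal dose are left out of the main durability summary, and that the all-samples result is shown as a sensitivity analysis. Report the number of such doses by arm, including when it is zero.

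**Cost.** A protocol amendment with ethics approval, one eCRF field at existing visits, some retrospective card checks, and a few samples lost from the main summary. No extra visit or blood draw is needed.
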